- Changes in C-SSRS during the course of the study indicating worsening should be evaluated by the investigator for clinical significance, and if clinically significant (e.g., alteration in medical care or intervention is required), an associated AE should be recorded, if present. The AE should be the primary underlying clinical manifestation assessed as clinically significant, and not the change in score itself.

Treatment emergent adverse events are defined as those that occur on or after the date of the first dose of double-blind investigational product.

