#### **8.3.2.1.3. Time Period and Frequency for Collecting Adverse Event and Serious Adverse Event Information**

Collection of AEs and SAEs will begin at the time a subject signs informed consent and continues until the follow-up phone call (Visit 7) as shown in the Time and Events Schedule (Section 8.1). SAEs that are spontaneously reported by the subject or subject representative or discovered by the investigator or designee after the follow-up phone call (Visit 7) and up to 30 days after the last dose of IP must be collected and reported.

All SAEs will be recorded and reported to the sponsor or sponsor’s representatives within 24 hours of the investigator becoming aware of the SAE according to Section 8.3.2.1.7.

Investigators are not obligated to actively seek AEs or SAEs in former study subjects. However, if the investigator learns of any SAE, including a death, at any time after a subject has been discharged from the study, and he/she considers the event reasonably related to the

investigational product or study participation, the investigator must promptly notify the sponsor or sponsor representative.

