4.1.5 Visits and Periods

There are 5 study periods during this study:

- The Screening Period is defined as the period of time prior to the subject receiving the first dose of single-blind placebo run-in medication.
- The Single-Blind Placebo Run-In Period (Period I) is defined as the period from the first dose of single-blind run-in medication and ends on the last dose date of single-blind run-in medication. The assessments taken on the date of the first dose of randomized double-blind investigational product will be assumed to have been completed before the first dose of double-blind investigational product and will be slotted to this period.
- The First Two-Week Double-Blind Treatment Period (Period II) starts on the date of first dose of double-blind investigational product and ends on the last dose date. If the first dose of randomized investigational product is taken on the same day as Visit 3 assessments, it will be assumed that the assessments were completed before the first dose of double-blind investigational product has been taken.
- The Single-Blind Placebo Washout Period (Period III) starts one day after the last dose of the double-blind medication has been taken in Period II and lasts until the first dose of the double-blind investigational product in Period IV. The assessments taken on the date of the first dose of randomized double-blind investigational product will be assumed to have been completed before the first dose of double-blind investigational product and will be slotted to this period.
- The Second Two-Week Double-Blind Treatment Period (Period IV) starts on the date of the first dose of double-blind investigational product and ends on the last dose date. If the first dose of randomized investigational product is taken on the same day as Visit 5 assessments, it will be assumed that the assessments were completed before the first dose of double-blind investigational product has been taken.

A safety follow-up telephone call will be conducted approximately 2 weeks after completion of Period IV.

Study visits will be determined from the scheduled times as reported on the CRF. As indicated in Table 1, Schedule of Assessments visit windows of +/- 3 days are allowed for scheduling purposes. For analysis purposes in this crossover study, no visit reassignment will be used even if a visit falls before or after the scheduling window.

Table 1: Schedule of Events

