4.3.1 Incomplete Dates for Concomitant Medication and Adverse Events

For analyses of AEs and concomitant medication usage, a complete date must be established in order to correctly identify the AE or medication as occurring during treatment or not. For purposes of imputing missing components of partially-reported start and stop dates for AEs and for medication use, the algorithms listed below will be followed. Start and stop dates of AEs or concomitant medication will be displayed as reported in the subject data listings (ie, no imputed values will be displayed in data listings).

Missing start day, but month and year present:

- If the occurrence of the AE/concomitant medication is in the same month and year as is the date of first dose of investigational product in Period II (which is the first Two-Week Double-Blind Treatment Period), then the start day of the event/concomitant medication will be assigned to the day of the first dose of investigational product taken in Period II.
- If the occurrence of the AE/concomitant medication is in the same month and year as is the date of the first dose of investigational product in period IV (which is the second Two-Week Double-Blind Treatment Period), then the start day of the event/concomitant medication will be assigned to the day of the first dose of investigational product taken in Period IV.
- If the dates of first dose of investigational product for Period II and for Period IV fall in the same month, then the start date day of the event/concomitant medication will be assigned to the day of the first dose of investigational product taken in Period II.
- Otherwise, the start day will be set to the 1st day of the month.

Missing start day and month, but year present:

- If the occurrence of the AE/concomitant medication is in the same year as is the date of first dose of investigational product in Period II (which is the first Two-Week Double-Blind Treatment Period), then the start day of the event/concomitant medication will be assigned to the day of the first dose of investigational product taken in Period II.
- If the occurrence of the AE/concomitant medication is in the same year as is the date of the first dose of investigational product in period IV (which is the second Two-Week

Double-Blind Treatment Period), then the start day of the event/concomitant medication will be assigned to the day of the first dose of investigational product taken in Period IV.

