7 SAFETY SUMMARIES AND ANALYSES

The safety analysis will be descriptive in nature, and will be presented for the Safety Population. All safety data collected and captured in the CRF will be included in data listings sorted by domain, sequence, subject, and time point, or as appropriate. Mean changes from pre-treatment to on-treatment (Periods II and IV together) will be tabulated by treatment, while the number of subjects with potentially clinically significant values at pre-treatment and at the end of each double-blind two-week treatment period (Period II and Period IV) will be presented.

Generally, safety data will be presented for the Placebo Run-In Period, for the Double-Blind Treatment Period by treatment group (Period II and Period IV plus 7 days after the end of these periods, for the Washout Period starting at day 8 of the Washout Period, and for the post-treatment Follow-up Period starting at day 8 of the Follow-up Period.

All safety data will be summarized overall and then by stratified subgroup: dementia type (AD, LBD) and baseline MMSE (14-19 and 20-26).

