7.1 Adverse Events

Adverse events will be classified using the MedDRA version 18.1 coding dictionary. Tabulations will include an overall incidence of at least one adverse event, incidence within system organ class (SOC), and incidence by preferred term. Each subject may only contribute once per treatment group, that is by first occurrence to each of the incidence rates, regardless of the number of occurrences, as follows:

- Adverse events occurring prior to the first dose of double-blind investigational product will be referred to as Treatment-Emergent AEs (TEAEs) and presented as Placebo Run-In events.
- Adverse events occurring on or after the first dose of each double-blind two-week treatment period (Period II and period IV), and within 7 days of the last dose of double-blind investigational product, will be referred to as TEAEs and presented by treatment group.
- Events occurring 7 days after the last dose of Period II and Period IV and for the post-treatment Follow-up Period starting at day 8 (up to 14 days post-last-dose) will be presented as Post-Treatment Period. These events will only be included in a data listing.

Tabulations of the incidence of AEs will be presented as follows:

- Overview of TEAE
- TEAE by SOC and preferred term
- TEAE by preferred term
- TEAE by SOC, preferred term, and relationship to study drug
- TEAE by SOC, preferred term, and maximum severity (mild, moderate, and severe)

All AEs will be listed with its relationship to study drug and severity, flagging those which are not events during treatment-emergent period.

A listing of all deaths and serious AEs will be provided. Any TEAE leading to study drug temporary and permanent discontinuation will also be listed.

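### SAP 7.1 calls adverse events before the first double-blind dose treatment-emergent, contrary to the protocol and undeclared, and states no start for the run-in category

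*SAP*

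**What the plan says.** The first bullet of SAP 7.1 states that "Adverse events occurring prior to the first dose of double-blind investigational product will be referred to as Treatment-Emergent AEs (TEAEs", and that they are "presented as Placebo Run-In events". It sets an upper limit in time and no lower one. The second bullet also uses the term TEAE, for events from the first dose of each double-blind period to 7 days after the last dose, shown by treatment group. The adverse event listing is to flag events outside the treatment-emergent period, a phrase that 7.1 does not define further.

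Four other places bear on this:

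- Protocol 8.3.2.1.1: "Treatment emergent adverse events are defined as those that occur on or after the date of the first dose of double-blind investigational product".
- Protocol 8.3.2.1.3: "Collection of AEs and SAEs will begin at the time a subject signs informed consent".
- SAP 4.1.5 separates two pre-randomization periods: "The Screening Period is defined as the period of time prior to the subject receiving the first dose of single-blind placebo run-in medication", and "The Single-Blind Placebo Run-In Period (Period I) is defined as the period from the first dose of single-blind run-in medication".
- The opening of SAP Section 7: "Generally, safety data will be presented for the Placebo Run-In Period", followed by the double-blind, washout and follow-up periods. Screening is not among them.

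SAP 4.2 gives the SAP precedence where it differs from the protocol's analysis. SAP Section 9 reports no meaningful change from the protocol.

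**The concern.** Treatment-emergent is the term on which the safety tables rest; every incidence tabulation listed in SAP 7.1 is a TEAE tabulation. If the governing document applies the term to events that the protocol excludes, two programmers working from the two documents would set different flags from the same data.

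The missing start date raises a second question. Events during screening, when the subject has taken no study tablet of any kind, could be displayed as having occurred on run-in placebo. SAP 7.1 gives screening events no category of their own.

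**Working it through.** The plan states no figure to reproduce, so the check is mainly a comparison of definitions.

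**1. Classification by onset**

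| Onset | Protocol 8.3.2.1.1 | SAP 7.1 as written | Period in SAP 4.1.5 |
|---|---|---|---|
| Consent to before first single-blind dose | Not a TEAE | TEAE, run-in event | Screening |
| First single-blind dose to before first double-blind dose | Not a TEAE | TEAE, run-in event | Period I |
| First double-blind dose onward, within the SAP windows | TEAE | TEAE, by treatment group | Period II or IV, plus 7 days |

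The label differs in both of the first two rows, so supplying a start date for the run-in does not remove the conflict with the protocol. Only the first row depends on whether SAP 7.1 is read alone or together with 4.1.5 and the opening of Section 7.

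**2. The listing flag.** If every event before double-blind dosing is a TEAE, none of them can be flagged as outside the treatment-emergent period. The flag would then apply only to post-treatment events.

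**3. Length of the literal window.** Screening lasts s = 0 to 28 days, or up to 28 + 14 = 42 with approval (Protocol 2 and 8.1). The run-in lasts r = 14 to 17 days (Protocol 8.1). Read literally, the run-in category covers s + r days, and the share before any tablet is s/(s + r):

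| s | r = 14 | r = 17 |
|---|---|---|
| 0 | 0/14 = 0% | 0/17 = 0% |
| 28 | 28/42 = 66.7% | 28/45 = 62.2% |
| 42 | 42/56 = 75.0% | 42/59 = 71.2% |

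These are shares of calendar time, not of events.

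**4. Partial dates once a start is set.** This step concerns the fix; it does not measure the defect. Under SAP 4.3.1, an event with unknown start day is moved to the first Period II or Period IV dose if that dose falls in the reported month. If neither does: "Otherwise, the start day will be set to the 1st day of the month". The first single-blind and first double-blind doses are taken in clinic at Visits 2 and 3 (Protocol 7.1). If Visit 2 is on day d of a month of L days, Visit 3 falls in the next month when d > L − r, which holds for r of the L dates. Assuming Visit 2 is equally likely on any date:

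- r = 14: from 14/31 = 45.2% to 14/28 = 50.0%.
- r = 17: from 17/31 = 54.8% to 17/28 = 60.7%.

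The smallest such d is 28 − 17 + 1 = 12. A run-in event reported only by month, in the Visit 2 month, would therefore be dated at least 11 days before the first single-blind dose, and a bare cut at that dose would file it under screening. The year-only rule acts the same way when Visit 2 falls in December and Visit 3 in January: the event goes to 1 January of the Visit 2 year.

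**The case against.** The best defense is that the SAP already supplies the start. SAP 7.1 calls these events run-in events, 4.1.5 starts the run-in at the first single-blind dose with screening as a separate period, and Section 7 presents safety data by that period. The table specifications are in a separate spreadsheet (SAP 1) that was not available and may set the bound. This largely stands. A reader might infer that the SAP flatly contradicts its own definition of Period I. It does so only if 7.1 is read in isolation; the fair statement is that the bound is implied and not stated.

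A second argument is that the label does little harm, because safety analysis is descriptive and run-in events are shown apart from double-blind events. That also stands. A reader might infer that the intepirdine and placebo comparison is contaminated; the second bullet of 7.1 assigns double-blind events by treatment group under its own window, so it is not. Nor do the percentages in step 3 show that run-in incidence is inflated by any amount, since the documents give no event rates. Part of the screening information is also routed elsewhere: clinically significant abnormal vital signs found at Visit 1 go to medical history (Protocol 8.3.2.3). Other screening events do not.

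A third argument is that the label has a use. It brings run-in events into the TEAE tables, and Protocol 10.4.1.1 requires a separate run-in summary. Placebo also counts as investigational product (Protocol 7.1), so the sponsor may have meant run-in placebo to count as treatment. This is a good reason not to remove the label without adding a run-in table. It does not excuse an undeclared change of definition.

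**Conclusion.** The point holds and is minor. The label in SAP 7.1 contradicts the protocol's definition on any reading, the SAP version would govern, and Section 9 does not declare it. The absence of a stated start is a lesser fault, because other SAP sections imply one.

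The effect is confined to three places: the run-in adverse event display, any TEAE count over all subjects combined (SAP 4.2 generally adds such a column), and the treatment-emergent flag in the listing. The double-blind columns are untouched. No change in incidence can be calculated. The documents do not show whether the wording is a slip or intended. The conclusion rests on the SAP text alone, without the table specifications.

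**What to change.** In SAP 7.1:

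- Define run-in events as those with onset on or after the first single-blind dose and before the first double-blind dose. Label them run-in AEs and tabulate them separately by system organ class and preferred term, which keeps the run-in summary required by Protocol 10.4.1.1 and SAP Section 7.
- List earlier events and flag them as pre-treatment.
- Reserve TEAE for events from the first double-blind dose, as in the protocol, or declare the different definition in Section 9.

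In SAP 4.3.1, add one rule for adverse events only. It applies if the start day, or day and month, is missing and the reported month or year is that of the first single-blind dose but contains neither the first Period II nor the first Period IV dose. Onset is then assigned to the first single-blind dose date. The Period II and Period IV rules stay as they are. The addition must not extend to medications, although 4.3.1 treats both together: SAP 5.7 uses the first single-blind dose to separate prior from concomitant medication, and the same imputation would shift that classification.

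The cost is some wording, a date condition, one imputation rule and one extra table. The downside is that some screening events with partial dates would be assigned to the run-in.

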#### **11.1.5. Study Files and Retention of Records**

The investigator must maintain adequate and accurate records to enable the conduct of the study to be fully documented and the study data to be subsequently verified. These documents should be classified into at least the following 2 categories: (1) investigator's study file, and (2) subject clinical source documents.

The investigator's study file will contain the protocol/amendments, eCRF and query forms, IRB or IEC and governmental approval with correspondence, informed consent, drug records, staff curriculum vitae and authorization forms, and other appropriate documents and correspondence.

The required source data should include sequential notes containing at least the following information for each subject:

- Documentation that subject meets eligibility criteria, i.e., history, physical examination, and confirmation of diagnosis (to support inclusion and exclusion criteria);
- Participation in trial (including trial number);
- Trial discussed and date of informed consent;
- Dates of all visits;
- Documentation that protocol specific procedures were performed;

- Results of safety parameters, as required by the protocol;
- Start and end date of investigational product (including dose regimen, dispensing and return);
- Record of all AEs (start and end date, causality and intensity);
- Concomitant medication (including start and end dates, dose, and dose changes);
- Date of trial completion and reason for early discontinuation, if applicable.

All clinical study documents must be retained by the investigator until at least 2 years after the last approval of a marketing application in an ICH region (i.e., United States, Europe, or Japan) and until there are no pending or contemplated marketing applications in an ICH region; or, if no application is filed or if the application is not approved for such indication, until 10 years after the investigation is discontinued and regulatory authorities have been notified. Investigators may be required to retain documents longer if required by applicable regulatory requirements, by local regulations, or by an agreement with Axovant Sciences. The investigator must notify Axovant Sciences before destroying any clinical study records.

Should the investigator wish to assign the study records to another party or move them to another location, Axovant Sciences must be notified in writing in advance.

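### SAP 7.1 has no rule for an adverse event that worsens in a later double-blind period, and its relationship table counts by first rather than strongest occurrence

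*SAP*

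**What the plan says.** SAP 7.1 sorts AEs into three groups by timing.

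- Events before the first double-blind dose "will be referred to as Treatment-Emergent AEs (TEAEs) and presented as Placebo Run-In events".
- The treatment groups receive "Adverse events occurring on or after the first dose of each double-blind two-week treatment period", through 7 days after the last double-blind dose.
- Later events, in washout or follow-up from day 8, form a post-treatment category: "These events will only be included in a data listing".

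On counting, the same section says: "Each subject may only contribute once per treatment group, that is by first occurrence to each of the incidence rates". The planned tables include "TEAE by SOC, preferred term, and relationship to study drug" and "TEAE by SOC, preferred term, and maximum severity (mild, moderate, and severe".

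The protocol's definition in 8.3.2.1.1 also rests on timing: "Treatment emergent adverse events are defined as those that occur on or after the date of the first dose of double-blind investigational product". Protocol 10.4.1.1 assigns each AE to a treatment by the last dose taken. None of these texts mentions an AE that starts earlier and becomes worse under a later treatment.

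**The concern.** Safety and tolerability is the only secondary objective, and AEs are its central measure. Every subject passes through a placebo run-in, a treatment period, a placebo washout and a second treatment period. A complaint can therefore begin in one phase and become more severe in another. If such an AE is held as one record and filed by its start, the increase in severity is not attributed to the treatment under which it happened.

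The SAP compares each period with its own starting point for other safety data. It does so through laboratory shifts and new-onset values (7.2), changes in vital signs and ECG (7.3, 7.4), and a listing of C-SSRS worsening between Visits 3 and 4 and between Visits 5 and 6 (7.6). AEs have no equivalent.

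A second matter sits in the same section. Severity is tabulated at its maximum, but nothing says that relationship to study drug is tabulated at its strongest, and the general rule is first occurrence.

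**Working it through.** The point concerns a definition, and the plan states no figure to reproduce. The check is a reading of the passages together, followed by a trace through both sequences.

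**1. What does *occurring* mean?** Two features favour onset: the first-occurrence counting rule, and the rules in SAP 4.3.1 that move partial AE start dates to the first double-blind dose. SAP 5.7 provides that a medication begun earlier and still ongoing is concomitant, and that it may count in several periods. AEs have no such provision. Against this, SAP 4.3.1 completes stop dates as well, and the SAP never uses the word onset in this rule. Onset is the likely reading, not a stated one.

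**2. Is a worsening a new AE?** Protocol 8.3.2.1.1 makes an exacerbation of a chronic or intermittent pre-existing condition, including greater intensity, an AE in its own right. It does not say whether an acute AE that arose in run-in, on double-blind treatment or in washout counts as pre-existing. Protocol 8.3.2.1.6 requires follow-up until the event resolves or stabilises, but does not say that a rise in severity opens a new record. Protocol 11.1.5 asks for "Record of all AEs (start and end date, causality and intensity", which is a minimum list for source notes. It does not describe the AE form.

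**3. Trace, taking *occurring* as onset and one record per AE.**

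| AE begins | AE worsens | Sequence | Where it is shown |
|---|---|---|---|
| Run-in | Period II or IV, either treatment | AB and BA | Run-in only |
| Placebo, Period II or the 7 days after | Intepirdine, Period IV | BA | Placebo |
| Intepirdine, Period II or the 7 days after | Placebo, Period IV | AB | Intepirdine |
| Washout, from day 8 | Intepirdine, Period IV | BA | Listing only |
| Washout, from day 8 | Placebo, Period IV | AB | Listing only |

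In rows 2 and 3 the maximum-severity table can credit the first treatment with a severity reached on the second.

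**4. Trace under the alternatives.** If the site records the worsening as a new exacerbation, its onset lies in the later period, so every row is counted for the treatment in use. If *occurring* means present, every row is again counted there. In that case an unchanged run-in AE that persists is also charged to each treatment.

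**5. Relationship table.** The protocol's causality scale (8.3.2.1.4) has five levels. Suppose a subject has two events of the same preferred term on the same treatment, the first judged unlikely and the second probable. Counting by first occurrence enters the subject as unlikely; counting by strongest relationship enters the subject as probable. The severity table already takes the worst grade.

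**6. Scale.** The documents give no AE rate, no proportion of AEs ongoing at a period's start and no rate of worsening, so the number of affected subjects cannot be calculated. The planned size is 30 to 40. If all subjects contribute to a treatment, one subject is 1/40 = 2.5% to 1/30 = 3.3% of its denominator.

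**The case against.** The strongest reply has four parts.

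- **The SAP does not say that an AE belongs only to the treatment under which it starts.** A reader might infer that, but the text leaves it open. This stands: the defect is a missing rule, with onset as the likely default. Reading the word as presence does not remove the need for a rule, as step 4 shows.
- **The protocol counts exacerbations as AEs.** A reader might infer that a worsening on intepirdine is never counted. The documents do not support that, because an exacerbation recorded as a new event is counted where it happens. What remains is an AE already on file that is not re-recorded, and for those the outcome depends on site practice.
- **The gap works in both directions.** A reader might infer that it only hides harm from intepirdine. Rows 1, 3 and 5 of the trace show the same loss or misattribution for worsening on placebo. The observed difference would shrink only if intepirdine worsened existing complaints more often than placebo, and the documents give no evidence on that.
- **The safety analysis is descriptive.** All AEs are listed with relationship and severity, deaths and serious AEs are listed, and 30 to 40 subjects can be reviewed individually. This limits the harm, but the summary tables would still differ from the listings.

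On the relationship table, counting once towards each incidence rate could mean that each causality level is its own rate, so that a subject appears under both unlikely and probable. That reading is possible. The SAP does not choose it, and under it no table would give each subject a single strongest relationship.

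**Conclusion.** The concern holds as a gap in the counting rules. SAP 7.1 and protocol 8.3.2.1.1 and 10.4.1.1 do not say how to treat an AE that begins earlier and worsens in a later double-blind period. On the likely onset reading, and where the worsening is not entered as a new event, it may be left out of that treatment's TEAE and maximum-severity tables. Either treatment can be affected, and the listings keep the events. Separately, first-occurrence counting can understate relatedness within a treatment, while severity is taken at its maximum.

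The conclusion rests on two assumptions: that *occurring* means onset, and that a rise in severity does not open a new record. The CRF is not among the documents, so the second cannot be checked. The overall size is not derivable; only the per-subject scale of 2.5 to 3.3 percentage points is. The primary gait-speed analysis is untouched. This is an inexpensive improvement that changes what the safety tables count.

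**What to change.** 1. In SAP 7.1, define a TEAE for a treatment as an AE that starts during Period II or IV or the following 7 days, or that increases in severity in that window from its level at that period's first dose. An ongoing, unchanged AE is then not charged again.
2. Add a CRF completion instruction to open a new record, linked to the existing one, when the severity of an AE on file increases.
3. In the relationship table, count each subject once per treatment at the strongest relationship within preferred term, within SOC and overall, matching the maximum rule for severity.
4. Align protocol 8.3.2.1.1 (both the exacerbation clause and the TEAE definition) and 10.4.1.1 with this rule.

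The cost is SAP wording, the matching protocol text and one instruction to sites. AE counts will be slightly higher on both treatments. Design, dosing and visit schedule do not change. If AE records are already complete without linked entries, item 2 cannot be applied to them; items 1 and 3 can still be specified before database lock, and the report should state the limit that this puts on detecting worsening.
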